APPENDIX 9. VISUAL ANALOGUE SCALE

Please place a vertical mark along the line where you feel the severity of your symptoms lie currently.

**APPENDIX 10. MINI RHINOCONJUNCTIVITIS QUALITY OF LIFE
QUESTIONNAIRE (MINIRQLQ)⁶⁶**

**MINI RHINOCONJUNCTIVITIS QUALITY
OF LIFE QUESTIONNAIRE (MiniRQLQ)**

**SELF-ADMINISTERED
UNITED KINGDOM VERSION**

© 1997

QOL TECHNOLOGIES LTD.

For further information:

[name], MCSP, MSc
Professor
[name]
[name]
[name]
[name]. UK
Telephone: [name]
Fax: [name]
E-mail: [contact]
Web: www.qoltech.co.uk

© The MiniRQLQ is copyrighted and all rights are reserved. No part of this questionnaire may be sold, modified or reproduced in any form without the express permission of [name] on behalf of QOL Technologies Limited. © 2006 QOL Technologies Limited.

MARCH 2006

MINI RHINOCONJUNCTIVITIS
QUALITY OF LIFE QUESTIONNAIRE
(ENGLISH FOR UK VERSION)
SELF-ADMINISTERED

PATIENT ID _____

DATE _____

Page 1 of 2

Please complete **all** questions by circling the number that best describes how **troubled** you have been during the **last week as a result of your nose/eye symptoms**.

Not
troubled

Hardly
troubled at all

Somewhat
troubled

Moderately
troubled

Quite a bit
troubled

Very
troubled

Extremely
troubled

ACTIVITIES

1. REGULAR ACTIVITIES
AT HOME AND AT
WORK
(your occupation or
tasks that you have to
do regularly around your
home and/or garden)

0 1 2 3 4 5 6

2. RECREATIONAL
ACTIVITIES
(indoor and outdoor
activities with friends
and family, sports, social
activities, hobbies)

0 1 2 3 4 5 6

3. SLEEP
(difficulties getting a
good nights sleep and/or
getting to sleep at night)

0 1 2 3 4 5 6

PRACTICAL PROBLEMS

4. NEED TO RUB
NOSE/ EYES

0 1 2 3 4 5 6

5. NEED TO BLOW NOSE
REPEATEDLY

0 1 2 3 4 5 6

MINI RHINOCONJUNCTIVITIS
QUALITY OF LIFE QUESTIONNAIRE
(ENGLISH FOR UK VERSION)
SELF-ADMINISTERED

PATIENT ID _____

DATE _____

Page 2 of 2

How **troubled** have you been during the **last week** as a result of these symptoms?

	Not troubled	Hardly troubled at all	Somewhat troubled	Moderately troubled	Quite a bit troubled	Very troubled	Extremely troubled
NOSE SYMPTOMS							
6. SNEEZING	0	1	2	3	4	5	6
7. STUFFY/BLOCKED NOSE	0	1	2	3	4	5	6
8. RUNNY NOSE	0	1	2	3	4	5	6
EYE SYMPTOMS							
9. ITCHY EYES	0	1	2	3	4	5	6
10. SORE EYES	0	1	2	3	4	5	6
11. WATERING EYES	0	1	2	3	4	5	6
OTHER SYMPTOMS							
12. TIREDNESS AND/OR FATIGUE	0	1	2	3	4	5	6
13. THIRST	0	1	2	3	4	5	6
14. FEELING IRRITABLE	0	1	2	3	4	5	6

APPENDIX 11. CSMS: SEASONAL WEEKLY COMBINED SYMPTOM MEDICATION SCORE

ITN084AD-Study		CONFIDENTIAL	
Participant Hospital Number	Participant Initials	Participant Study Number	Date (dd/mm/yyyy)
			□□/□□□□/202□
			CSMS

CSMS: Seasonal weekly Combined Symptom Medication Score:

Please complete the questions and the visual analogue scale below every Wednesday throughout the hay fever season. Your answers should refer only to the full week before you complete it. Please hand back the paper sheet to a member of the team at your next visit.

Over the past week, how often have you used your rescue medication for your hay fever? Please circle the appropriate answer, to the best of your knowledge / memory:	
Antihistamines (Desloratadine tablets and/or Opatanol eye drops)	
	SCORE (please circle one number)
Not used this week.....	0
On 1 day this week.....	1
On 2 days this week.....	2
On 3 days this week.....	3
On 4 days this week.....	4
On 5 or more days this week.....	5
Nasal spray (Mometasone)	
	SCORE (please circle one number)
Not used this week.....	0
On 1 day this week.....	1
On 2 days this week.....	2
On 3 days this week.....	3
On 4 days this week.....	4
On 5 or more days this week.....	5

Please place a vertical mark along the line to reflect the severity of your hay fever this last week.

0	10
No symptoms	Worst possible symptoms
	

(For Office Use)	
Weekly VAS score 	Weekly total medication score (WMS) 
Weekly Combined Symptom & Medication Score $= (VAS + WMS) / 2$ 	

Name, Signature and Date of the person completing the form:

Name: _____ Signature: _____ Date: □□/□□□□/202□

Data source-CSMS-v1-06Jul2020. Please keep in patient hospital record

1

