5.3 RISKS OF OTHER PROTOCOL SPECIFIED MEDICATIONS

Besides Dupixent® and Grazax®, other protocol specified medications would include oral/ocular antihistamines; oral, nasal, and inhaled corticosteroids; and combination inhaled long-acting beta agonists with corticosteroids. Ocular antihistamines may rarely be associated with local irritation. Oral antihistamines may be associated with drowsiness. Nasal steroids may be associated with local irritation, sneezing, and rhinorrhea. Minor nasal bleeding may also occur. Inhaled corticosteroids may be associated with cough, hoarseness, and oral candidiasis. Rarely, systemic absorption of inhaled corticosteroids may lead to the side effects listed below under oral corticosteroids. Inhaled beta agonists may be associated tachycardia, palpitations, tremor, headache, hypokalemia, and elevations in serum glucose. Oral steroids when used continuously for prolonged periods of time (>2 weeks) may be associated with adrenal insufficiency, skin atrophy, osteoporosis, hypertension, diabetes, glaucoma, cataracts, dyspepsia and mood changes. However, in this trial, only short courses (up to 7 days) of oral corticosteroids will be dispensed and only after consultation with the study clinician and monitoring. Very few participants are likely to require systemic corticosteroids as rescue medication.

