7. OTHER MEDICATIONS

7.1 CONCOMITANT MEDICATIONS

Use of the following rescue medications is permitted. These medications are considered standard of care and will be provided by the study approximately 2 weeks before the start of the pollen season and throughout the pollen season:

- Antihistamine tablets (desloratidine)
- Nasal corticosteroid spray (fluticasone propionate aqueous nasal spray)
- Ophthalmic antihistamine drops (olopatadine)
- Short-acting beta2-agonist inhaler (albuterol)

Use of the following rescue medications will be provided only after participants are evaluated by a study clinician. Evaluations may occur by phone contact or clinic visit.

- Oral corticosteroid (prednisolone 5mg tablets)
- Corticosteroid inhaler (fluticasone propionate)
- Combination of long-acting beta-agonist and corticosteroid inhaler (salmeterol/fluticasone)

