9.2.6. Seasonal outcome 1: Weekly seasonal symptoms VAS 0-10, Medication scores, and CSMS

Weekly seasonal symptoms (Visual Analogue Scale [VAS] 0-10 cm), medication scores, and combined symptom medication score (CSMS) were collected over the course of 10 weeks from approximately the end of May through end of July, for each year of the study:

- 2021 (baseline season)
- 2022 (year 1)
- 2023 (year 2)
- 2024 (year 3)

Within a given year, the definition of a pollen season will be programmatically derived using Protocol Table 6 as shown below:

	Pollen Season	Peak pollen season	High pollen days
Start of season	1st day of 5 days (out of 7 consecutive days) each of these 5 days with ≥ 3 pollen/m ³ and with a sum of these 5 days of ≥ 30 pollen/m ³	1st day of 3 consecutive days, each with at least ≥ 50 pollen/m ³	The day(s) with at least 50 pollen/m ³
End of season	Last day of series of 5 days (out of 7 consecutive days) with ≥ 3 pollen/m ³ and with a sum of these 5 days of ≥ 30 pollen/m ³	Last day of at least 3 consecutive days, each with ≥ 50 pollen/m ³	

The following two timeframes will be used for analysis:

- only the values collected during weeks which are determined to be “in-season” according to the above table’s definition of “Pollen Season”
- all data collected i.e. up to 10 values per participant per year

The main model for analyses (including for the key secondary endpoint of CSMS) will estimate treatment effects from only the “in-season” weeks, whereas supportive analysis models will use all data collected.

The following three outcomes will be analyzed separately:

- VAS score
- Medication score
- CSMS (combination of VAS and medication score)

The score for each outcome will be analyzed for each of the 10 weeks at each year (including the baseline year). A multiple imputation (MI) approach, similar to the approach described in [Section 9.1.3](#) above, will be used to fill in missing values prior to modelling the score of each outcome at each week per year. Missing at random (MAR) will be assumed given the sporadic missingness of the values at each week.

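### The CSMS form and Protocol 7.1 name different rescue nasal sprays, the form gives no points for the permitted oral corticosteroid, and SAP 9.2.6 settles neither

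*Protocol*

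**What the plan says.** Protocol 7.1 lists "Nasal corticosteroid spray (fluticasone propionate aqueous nasal spray") among the rescue medications that "will be provided by the study approximately 2 weeks before the start of the pollen season and throughout the pollen season". It is the only nasal spray listed there. A second list in 7.1, open to participants only after a study clinician has evaluated them, includes "Oral corticosteroid (prednisolone 5mg tablets"). Protocol 5.3 adds that "only short courses (up to 7 days) of oral corticosteroids will be dispensed" and expects hardly any participants to need systemic corticosteroid.

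The CSMS form in Appendix 11 has two medication items: "Antihistamines (Desloratadine tablets and/or Opatanol eye drops") and "Nasal spray (Mometasone"). Each is scored 0 to 5 by days of use, with 5 meaning "On 5 or more days this week". The weekly CSMS is the VAS plus the weekly medication score (WMS), divided by 2. The form has no item for oral corticosteroid.

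SAP 9.2.6 describes the outcome only as "CSMS (combination of VAS and medication score"). It gives no item list, no formula for the medication score and no rule for corticosteroid weeks. SAP 13 replaces the seasonal AUC by a mean but does not touch the scoring. SAP 8.5 (Table 2) places CSMS at year 3 in the survey questionnaire sub-family, tested by Hochberg at its own alpha of 0.05.

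**The concern.** A combined score is meant to stop rescue medication from passing as treatment benefit. That works only if the rescue drugs in use are counted.

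There are two gaps. First, the spray item carries half of the medication points and names a product absent from the rescue list in 7.1. The documents do not say how use of another spray is entered. Second, a permitted systemic rescue drug earns no points. If it relieves symptoms, the VAS falls and nothing in the score offsets that fall.

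What is at stake is the interpretation of one alpha-controlled key secondary endpoint, and of the medication score that SAP 9.2.6 also analyses separately. The primary endpoint, TNSS AUC after nasal challenge, does not use this form.

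**Working it through.** The documents give no CSMS standard deviation, effect size or power, so there is no planned figure to reproduce. The check applies the form's own formula.

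**Inputs**
- Antihistamine item A and spray item N, each 0 to 5 (Appendix 11).
- CSMS = (VAS + WMS)/2 (Appendix 11).
- WMS = A + N. This is an assumption: the form asks for a total but does not print the sum. It gives WMS 0 to 10 and CSMS 0 to 10.
- Up to 10 weekly scores per year, with the main analysis averaging in-season weeks (SAP 9.2.6). The number of in-season weeks W is not fixed; 6 to 10 is assumed.
- 30 participants per arm at year 3 (Protocol 13.6).
- All VAS values below are illustrative assumptions.

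**Spray item**
1. If use is not recorded under the item, CSMS falls by N/2, at most 5/2 = 2.5, whatever the VAS.
2. Example at VAS 6 with both items at maximum: (6 + 10)/2 = 8.0. The same week with the spray circled 0: (6 + 5)/2 = 5.5.
3. If a fraction f of an arm loses d item points in every week, the arm mean falls by f × d/2:
   - f = 0.10, d = 1: 0.05
   - f = 0.25, d = 3: 0.375
   - f = 1, d = 5: 2.5
4. The unadjusted contrast between two arms shifts by (f₁d₁ − f₂d₂)/2. This is zero when the loss is equal in both arms.

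**Oral corticosteroid**

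The reference is the 8.0 week above, and the VAS is assumed to fall to 2 on prednisolone.

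| Other rescue that week | CSMS | Drop from 8.0 |
|---|---|---|
| Continued and fully scored | (2 + 10)/2 = 6.0 | 2.0 |
| All stopped | (2 + 0)/2 = 1.0 | 7.0 |

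One such week in W lowers that participant's seasonal mean by drop/W:
- 2-point drop: 2/10 = 0.20 to 2/6 = 0.33.
- 7-point drop: 7/10 = 0.70 to 7/6 = 1.17.

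Dividing by 30 gives the shift in the arm mean per affected participant-week: 0.20/30 = 0.007 at the low end and 1.17/30 = 0.039 at the high end. Three such participants in one arm would move its mean by 0.02 to 0.12.

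**The case against.** The strongest reply is that the spray loss is conjecture. The form's question is about rescue medication in general, and 7.1 lists only one nasal spray, so a participant would naturally answer the spray item for whatever spray they had. Protocol 8.3.4 also allows a mobile application, so the wording participants saw is not known. This stands. The loss is possible under a literal reading of the item, but nothing shows that it occurred.

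A reader might infer that 7.1 records what was dispensed and the form is wrong. The documents do not settle this. The form is a trial-specific sheet, and the error could equally lie in 7.1, in which case no points are lost. All that can be said is that the passages conflict.

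A reader might also take the fall from 8.0 to 1.0 as typical of a prednisolone week. It rests on assumed VAS values and on all other rescue stopping, which no passage says. With other rescue continued and scored, the week scores 6.0.

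Nor do the documents support reading this as a route to a false positive for the combination. Scoring is the same in all blinded arms, so a biased contrast needs unequal rescue use. If double-placebo uses more, that arm's CSMS is lowered and the difference shrinks. The baseline-season score is a model covariate, which would absorb part of a stable reporting habit.

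Partial safeguards exist. VAS and medication score are analysed separately (SAP 9.2.6), heavy antihistamine use still scores 5, and concomitant medications are recorded with indications (Protocol 8.3.1) and start and stop dates (SAP 6.3). None of these defines the score or resolves the conflict.

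**Conclusion.** The contradiction on the spray and the missing oral corticosteroid item are both in the text, and nothing in the protocol or SAP resolves them.

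The spray point has the larger potential size: up to 2.5 of 10 CSMS points in an affected week, taking WMS as the sum of the two items, and conditional on use of the supplied spray not being recorded under the named item. How often that happened, if at all, cannot be told from the documents.

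The oral corticosteroid point is certain as an omission but small on average, at about 0.007 to 0.039 on an arm mean per affected participant-week, with very few users expected. It matters mainly for the individual weeks concerned.

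The direction of any bias depends on which arm uses more rescue. Greater use in double-placebo is plausible but is an assumption, and it would pull the contrast toward no effect. This is worth correcting for an alpha-controlled endpoint. It does not threaten the trial's primary conclusion.

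**What to change.** 1. Reconcile Protocol 7.1 and Appendix 11 on the nasal spray. Which product is correct is for the sponsor to establish.
2. Word or score the spray item as days of use of any nasal corticosteroid spray.
3. Define WMS in SAP 9.2.6 as the sum of the two items, and keep the form's score as the main analysis.
4. Add a prespecified sensitivity analysis in which weeks with systemic corticosteroid for hay fever, identified from the dated concomitant-medication records, receive an unfavourable medication score, for example the maximum of 10. That raises an affected week by (10 − WMS)/2: 5.0 points if no other rescue was scored, and nothing if both items were already at maximum.

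The note at the end of the SAP was written after database lock, so rewording the form may no longer be possible. If data collection is over, document how spray use was in fact recorded and report the sensitivity analysis labelled as added later.

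The cost is a clarification, one SAP definition and a small extra analysis on data already collected. The value of 10 is an arbitrary weight, which is why it belongs only in the sensitivity analysis.

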APPENDIX 12. GLOBAL EVALUATIONS NO. 1 AND 2**Global Evaluation No. 1**

The participant should be asked: "How do you assess the severity of your hay fever symptoms overall during this grass pollen season (Tick each single symptom)?"

Rhinoconjunctivitis/ Hay fever symptom		Symptoms			
		0 (None)	1 (Mild)	2 (Moderate)	3 (Severe)
Nasal symptoms					
1.	Runny nose				
2.	Blocked nose				
3.	Sneezing				
4.	Itchy nose				
Eye symptoms					
1.	Itchy eyes				
2.	Watery eyes				

Global Evaluation No. 2

The participant should be asked: "How was your hay fever this year compared with years before you started immunotherapy treatment (Tick only one)?"

Assessment						
Much better (+3)	Better (+2)	A little better (+1)	The same (0)	A little worse (-1)	Worse (-2)	Much worse (-3)
						

APPENDIX 13. MODIFIED RHINITIS SYMPTOM UTILITY INDEX

MODIFIED RHINITIS SYMPTOM UTILITY INDEX			
Participant's Initials ____	Staff's Initial's ____	Completion Date ____/____/____	Visit ____

[Interview] "I would like to ask about symptoms you may have had DURING THE PAST 2 WEEKS from [your/his/her] nose and eyes, how frequently you had these symptoms, and how bothered by these symptoms you were."

1. How many days have you had a stuffy or blocked nose during the past 2 weeks?

None.....0 [SKIP TO 3]
 1-3 days.....1
 4-7 days.....2
 8-14 days.....3

2. On average, how bothersome was your stuffy or blocked nose during the past 2 weeks?

Not bothered at all.....0
 Somewhat bothered.....1
 Bothered a lot.....2

3. How many days have you had a runny nose during the past 2 weeks?

None.....0 [SKIP TO 5]
 1-3 days.....1
 4-7 days.....2
 8-14 days.....3

4. On average, how bothersome was your runny during the past 2 weeks?

Not bothered at all.....0
 Somewhat bothered.....1
 Bothered a lot.....2

5. How many days have you had sneezing during the past 2 weeks?

None.....0 [SKIP TO 7]
 1-3 days.....1
 4-7 days.....2
 8-14 days.....3

6. On average, how bothersome was your sneezing during the past 2 weeks?

Not bothered at all.....0
 Somewhat bothered.....1
 Bothered a lot.....2

7. How many days have you had itching, watery eyes during the past 2 weeks?

None.....0 [SKIP TO 9]
 1-3 days.....1
 4-7 days.....2
 8-14 days.....3

8. On average, how bothersome were your itching, watery eyes during the past 2 weeks?

Not bothered at all.....0
 Somewhat bothered.....1
 Bothered a lot.....2

9. How many days have you had itching nose or throat during the past 2 weeks?

None.....0 [SKIP TO 11]
 1-3 days.....1
 4-7 days.....2
 8-14 days.....3

10. On average, how bothersome was your itching nose or throat during the past 2 weeks?

Not bothered at all.....0
 Somewhat bothered.....1
 Bothered a lot.....2

MODIFIED RHINITIS SYMPTOM UTILITY INDEX HANDCARD

Handcard One: Questions 1, 3, 5, 7, 9

None.....0
 1-3 days.....1
 4-7 days.....2
 8-14 days.....3

Handcard Two: Questions 2, 4, 6, 8, 10

Not bothered at all.....0
 Somewhat bothered.....1
 Bothered a lot.....2

APPENDIX 14. WAO SUBCUTANEOUS IMMUNOTHERAPY SYSTEMIC REACTION GRADING SYSTEM

World Allergy Organization Subcutaneous Immunotherapy Systemic Reaction Grading System (see text)				
Grade 1	Grade 2	Grade 3	Grade 4	Grade 5

Symptom(s)/ sign(s) of one organ system present¹
 
Cutaneous
 
Generalized pruritus, urticaria, flushing or sensation of heat or warmthⁱⁱ
 
or
 
Angioedema (not laryngeal, tongue or uvular)
 
or
 
Upper respiratory
 
Rhinitis (e.g., sneezing, rhinorrhea, nasal pruritus and/or nasal congestion)
 
or
 
Throat-clearing (itchy throat)
 
or
 
Cough perceived to come from the upper airway, not the lung, larynx, or trachea
 
or
 
Conjunctival
 
Conjunctival erythema, pruritus or tearing
 
Other
 
Nausea, metallic taste, or headache
	
Symptom(s)/ sign(s) of more than one organ system present
 
or
 
Lower respiratory
 
Asthma: cough, wheezing, shortness of breath (e.g., less than 40% PEF or FEV1 drop, responding to an inhaled bronchodilator)
 
or
 
Gastrointestinal
 
Abdominal cramps, vomiting, or diarrhea
 
or
 
Other
 
Uterine cramps
	
Lower respiratory
 
Asthma (e.g., 40% PEF or FEV1 drop, NOT responding to an inhaled bronchodilator)
 
or
 
Upper respiratory
 
Laryngeal, uvula or tongue edema with or without stridor
	
Lower or Upper respiratory
 
Respiratory failure with or without loss of consciousness
 
or
 
Cardiovascular
 
Hypotension with or without loss of consciousness
	
Death

Patients may also have a feeling of impending doom, especially in grades 2, 3, or 4.
 
Note: children with anaphylaxis seldom convey a sense of impending doom and their behavior changes may be a sign of anaphylaxis, e.g., becoming very quiet or irritable and cranky.

1. LIST OF ABBREVIATIONS

Table 1: List of Abbreviations

Abbreviation	Term
AE	Adverse event
ARIA	Allergic Rhinitis and its Impact on Asthma
AUC	Area under the curve
BDR	Biomarker and Discovery Research
BiG	Bioinformatics Groups
CRF	Case report form
CSMS	Combined Symptom Medication Score
CSR	Clinical Study Report
DSMB	Data and Safety Monitoring Board
eCRF	Electronic case report form
FEV1	Forced expiratory volume in one second
ICH	International Conference on Harmonization
IgE	Immunoglobulin E
ITN	Immune Tolerance Network
ITT	Intent-to-treat
MAR	Missing at Random
MCMC	Markov Chain Monte Carlo
MedDRA	Medical Dictionary for Regulatory Activities
MI	Multiple imputation
MiniRQLQ	Mini Rhinoconjunctivitis Quality of Life Questionnaire
mITT	Modified intent-to-treat
MNAR	Missing Not at Random
MRSUI	Modified Rhinitis Symptom Utility Index
NAC	Nasal allergen challenge
NIAID	National institute of allergy and infectious disease
PNIF	Peak nasal inspiratory flow
PP	Per protocol
REML	Restricted Maximum Likelihood

DAIT NIAID Immune Tolerance Network
Statistical Analysis Plan - ITN084AD GRADUATE

SAE	Serious adverse event
SAP	Statistical analysis plan
SD	Standard deviation
SLIT	Sublingual Immunotherapy
SOC	System organ class
SQ	Standardized Quality
TNSS	Total Nasal Symptom Score (0-12)
VAS	Visual analogue scale
WAO	World Allergy Organization

2. PURPOSE OF THE ANALYSES

The purpose of this Statistical Analysis Plan (SAP) is to describe the planned efficacy and safety analyses as well as data displays to be submitted for publication and/or included in the Clinical Study Report (CSR) for Protocol ITN084AD. This document provides details on the analysis populations, derivation of variables, plans for the handling of missing data, and statistical methods to be used in these analyses.

The statistical analysis plan (SAP) is based on International Conference on Harmonization (ICH) guidelines E3 (Structure and Content of Clinical Study Reports) and E9 (Statistical Principles for Clinical Trials).

This statistical analysis plan (SAP) only includes analyses related to the clinical endpoints. Mechanistic analyses will be performed at the Immune Tolerance Network (ITN), and a separate analysis plan may be created to detail the planned analyses. Relevant clinical data from the study will be submitted to the ITN Biomarker and Discovery Research (BDR) and ITN Bioinformatics Groups (BiG) to augment the mechanistic analyses.

3. PROTOCOL SUMMARY

Title	Grass Pollen Sublingual Tablet Immunotherapy plus Dupilumab for Induction of Tolerance in Adults with Moderate to Severe Seasonal Allergic Rhinitis
Short Title	Grass Pollen Immunotherapy plus Dupilumab for Tolerance Induction.
Clinical Phase	Phase II
Number of Sites	1 site
CTA Sponsor/Eudra Number	DAIT NIAID, 2018-003456-20
Study Objectives	The primary objective is to compare the effect of the combination of SLIT and dupilumab versus double placebo on the nasal allergen challenge (NAC) response to grass pollen at year 3, one year after completion of study treatment.
Study Design	
This is a randomized, double blinded trial in adults (n=108) with moderate to severe seasonal allergic rhinitis with allergic sensitization to grass pollen.
 
Participants will be recruited from October 2020 through May 2021. Eligible participants will be randomized to one of the following 3 groups in a 1:1:1 ratio.
 
• Combination of SLIT and dupilumab (n=36)• SLIT plus dupilumab placebo (n=36)• SLIT placebo plus dupilumab placebo (n=36)

	
Grazax[®] is a sublingual grass immunotherapy product approved for clinical use in the United Kingdom and will be used as SLIT in this study. It (and its matching placebo) will be self-administered daily by participants through week 104. Dupixent[®] is the brand name for dupilumab and is a monoclonal antibody against the IL-4 receptor. Dupilumab and its placebo will be administered every two weeks by subcutaneous injection through week 104. With appropriate training by study personnel, alternate doses of dupilumab (and other occasional doses as required) may be self-administered by participants at home. Dupilumab is approved for self-administration by patients. The treatment phase of 104 weeks will be followed by an observation phase of 52 weeks.

Primary Endpoint	
NAC (TNSS Area-under-Curve [AUC_{0-1hr}]) at year 3, one year after completion of treatment. The primary comparison will be between the combination of SLIT and dupilumab arm and the double-placebo arms (clinical tolerance endpoint).

Secondary Endpoint(s)	
Clinical tolerance endpoints at year 3, one year after completion of study treatment. The comparison will be between the combination of SLIT and dupilumab and the double-placebo arms.
 
 1. Peak nasal inspiratory flow (Delta PNIF AUC_{0-1hr}) 2. Peak NAC TNSS (0-1hr) 3. Size of early and late intradermal skin test response 4. Size of the skin prick test endpoint titration response 5. Seasonal outcomes 
 1. Weekly seasonal symptoms (Visual Analogue Scale [VAS] 0-10 cms) and combined symptom medication scores (CSMS) 2. Weekly rhinitis quality of life scores (Juniper mini-Rhinoconjunctivitis Quality of Life Questionnaire [miniRQLQ]) measured in-season 3. Modified Rhinitis Symptom Utility Index (MRSUI) measured in-season and out-of-season 4. Global Evaluations No. 1 and No. 2 after the season 
Clinical desensitization endpoints at year 1 and 2 whilst on study treatment. The comparison will be between the combination of SLIT and dupilumab and the double-placebo arms.
 
 6. TNSS AUC_{0-1hr} 7. Delta PNIF AUC_{0-1hr} 8. Size of early and late intradermal skin test response 9. Size of skin prick test endpoint titration response

	
10. Seasonal outcomes
 
 1. Weekly seasonal symptoms (VAS 0-10 cms) and CSMS 2. Weekly rhinitis quality of life scores miniRQLQ measured in-season 3. MRSUI measured in-season and out-of-season 4. Global Evaluations No. 1 and No. 2 after the season 
Safety Endpoints
 
The number, severity, and relatedness of local and systemic AEs and SAEs reported during screening, at baseline, during years 1 and 2 whilst on study treatment, and during year 3 (one year after completion of study treatment). Each treatment arm will be summarized separately.

Exploratory Endpoints	
Clinical tolerance endpoints at year 3, one year after completion of study treatment. All pairwise comparisons not included in primary and secondary endpoints above will be reported.
 
 1. TNSS AUC_{0-1hr} 2. Peak TNSS 3. Total sneeze count (0-15 minutes) from NAC 4. Delta PNIF AUC_{0-1hr} 5. Size of early and late intradermal skin test response 6. Size of skin prick test endpoint titration response 7. Seasonal outcomes 
 1. Weekly seasonal symptoms VAS 0-10 cms and CSMS 2. Weekly rhinitis quality of life scores miniRQLQ measured in-season 3. MRSUI measured in-season and out-of-season 4. Global Evaluations No. 1 and No. 2 after the season 
Clinical desensitization endpoints at year 1 and 2 whilst on study treatment. All pairwise comparisons not included in primary and secondary endpoints above will be reported.
 
 8. TNSS AUC_{0-1hr} 9. Delta PNIF AUC_{0-1hr} 10. Size of early and late intradermal skin test response 11. Size of skin prick test endpoint titration response 12. Seasonal outcomes 
 1. Weekly seasonal symptoms VAS 0-10 cms and CSMS

	
 2. Weekly rhinitis quality of life scores miniRQLQ measured in-season 3. MRSUI measured in-season and out-of-season 4. Global Evaluations No. 1 and No. 2 after the season 
Mechanistic endpoints at year 3, one year after study treatment (i.e., immune tolerance) and at year 1 and 2 whilst on study treatment (i.e., immune desensitization). All pairwise comparisons will be reported.
 
 13. Mechanistic assessments of local immune responses in the nasal mucosa before and after the NAC. 14. Mechanistic assessments of peripheral blood leukocytes (including eosinophils, mast cells, and basophils) and mononuclear cell subsets after the NAC. 15. Mechanistic assessments of local immune responses and peripheral blood leukocytes (including eosinophils, mast cells, and basophils) and mononuclear cell subsets during natural allergen exposure In versus Out of the pollen season.
Accrual and power calculation	
90 of the 108 enrolled participants will complete the study assuming approximately a 16.6% dropout rate.
 
Sample size for this trial was determined by calculating the total enrollment necessary to provide at least 80% power to detect an expected difference in the mean TNSS AUC_{0-1hr} at year 3 comparing the combination of SLIT and dupilumab arm to the double-placebo arm.

Study Duration	
4 years, Oct 2020 - Jan 2025.
 
 • Recruitment/screening: 11 months • Dosing: 28 months • Follow-up: 12 months
Treatment Description	
Participants will receive daily sublingual Grazax[®] 75,000 SQ units (containing 15 mcg major allergen Phl p 5) or placebo tablets once daily and Dupixent[®] 300mg or placebo subcutaneous injection every two weeks for 2 years.

Inclusion Criteria	
Individuals who meet all of the following criteria are eligible for enrollment as study participants:
 
 1. Participant must be able to understand and provide informed consent. 2. Adults age 18 to 65 years.

	
 3. A clinical history of grass pollen-induced allergic rhinoconjunctivitis for at least 2 years with peak symptoms in May, June, or July. 4. A clinical history of moderate to severe rhinoconjunctivitis symptoms for at least 2 years interfering with usual daily activities or with sleep as defined according to the Allergic Rhinitis and its Impact on Asthma (ARIA) classification of rhinitis. 5. A clinical history of inadequately controlled rhinoconjunctivitis symptoms despite treatment with antihistamines and/or nasal corticosteroids during the grass pollen season for at least 2 years. 6. Positive skin prick test response at screening, defined as wheal diameter greater than or equal to 3 mm, to Phleum pratense. 7. Positive specific IgE at screening, defined as greater than or equal to IgE class 2 (0.7 kU/L) against Phleum pratense. 8. A positive response to NAC with Phleum pratense defined as a TNSS greater than or equal to 5 of 12 points. Note this criterion was removed in protocol version 3.0. 9. A woman of childbearing potential (WOCBP; for definition, see Appendix 6 of protocol), regardless of birth control history is required to consistently use one of the following highly effective methods of contraception throughout the study: hormonal (e.g. oral, transdermal, intravaginal, implant, or injection); intrauterine device (IUD) or system (IUS); vasectomized partner; bilateral tubal occlusion; or sexual abstinence (for definitions see contraceptive guidance in Appendix 6 of protocol).
Exclusion Criteria	
Individuals who meet any of these criteria are not eligible for enrollment as study participants:
 
 1. Inability or unwillingness of a participant to give written informed consent or comply with study protocol. 2. Prebronchodilator forced expiratory volume (FEV₁) less than 70% of predicted value at either screening or baseline visit. 3. A clinical history of asthma requiring regular inhaled corticosteroids for > 4 weeks per year outside of the grass pollen season. 4. A clinical history of moderate to severe allergic rhinitis, as defined according to the ARIA classification of rhinitis, caused by either: 
 a. an allergen to which the participant is regularly exposed OR b. tree pollen during tree pollen season treated with regular antihistamine or intranasal corticosteroids.

	
 5. History of emergency visit or hospital admission for asthma in the previous 12 months. 6. History of chronic obstructive pulmonary disease. 7. History of recurrent acute sinusitis, defined as 2 episodes per year for the last 2 years, all of which required antibiotic treatment. 8. History of chronic sinusitis, defined as sinus symptoms lasting greater than 12 weeks that includes 2 or more major factors or 1 major factor and 2 minor factors. Major factors are defined as facial pain or pressure, nasal obstruction or blockage, nasal discharge or purulence or discolored postnasal discharge, purulence in nasal cavity, or impaired or loss of smell. Minor factors are defined as headache, fever, halitosis, fatigue, dental pain, cough, and ear pain, pressure, or fullness. 9. History of systemic disease affecting the immune system such as autoimmune diseases, immune complex disease or immunodeficiency. 10. Current symptoms of, or treatment for, upper respiratory tract infection, acute sinusitis, acute otitis media, or other relevant infectious process; serous otitis media is not an exclusion criterion. Participants may be re-evaluated for eligibility after symptoms resolve. 11. A past history of any malignant disease in the previous 5 years. 12. Any tobacco smoking within the last 6 months, or a history of greater than or equal to 10 pack years of cigarette use. Any vaping or electronic cigarette use within the last 6 months. 13. Previous immunotherapy with grass pollen allergen within the previous 5 years. 14. Previous treatment by dupilumab. 15. Previous Grade 4 anaphylaxis (WAO grading criteria) due to any cause. 16. History of anti-IgE, anti-IL-5, anti-IL-5 receptor, anti-IL-4/IL-13 receptor, or other monoclonal antibody treatment. 17. Current use of tricyclic antidepressants or monoamine oxidase inhibitors. 18. Ongoing systemic immunosuppressive treatment. 19. History of intolerance to the study therapy, rescue medications, or their excipients. 20. A positive pregnancy test. 21. Currently lactating/breast feeding.
--	--

	
22. The use of any investigational drug within 30 days of the screening visit.
 
23. The presence of any medical condition that the investigator deems incompatible with participation in the trial.
 
24. Past or current medical problems or findings from physical examination or laboratory testing that are not listed above, which, in the opinion of the investigator, may pose additional risks from participation in the study, may interfere with the participant's ability to comply with study requirements or may impact the quality or interpretation of the data obtained from the study.
 
25. Eosinophilic esophagitis or a diagnosis of any hypereosinophilic syndrome.
 
26. Administration of live attenuated vaccines within four weeks of dupilumab or dupilumab placebo injections, before the first injection and throughout the treatment period.

Study Stopping Rules	
 Any death that is possibly related or related to one of the investigational products (dupilumab/dupilumab placebo or SLIT/SLIT placebo) or a study procedure. Any grade 4 AE that is possibly related or related to one of the investigational products (dupilumab/dupilumab placebo or SLIT/SLIT placebo) or a study procedure. Any grade 3 AE that is possibly related or related to one of the investigational products (dupilumab/dupilumab placebo or SLIT/SLIT placebo) or a study procedure in three or more participants.

